## 9.7 Correlative Biomarker Analysis

Tumor and blood samples will be assessed for response and immune activation using: histopathology including immunohistochemistry, flow cytometry, NanoString, Multispectral analysis. Analysis will include: tumor response/viability, cytokine profile changes, T-cell population changes, and RNA level changes.

## 9.8 Complete Surgical Resection

Patients will be assessed at surgery to determine if complete surgical resection was achievable after neo-adjuvant treatment with nivolumab and HF10. Completeness of surgical resection will be defined by standard definitions as follows: R0 indicates all gross clinical disease resected with microscopic pathologic negative margins; R1 indicates all gross clinical disease; R2 indicates inability to completely excise all clinical disease (i.e. gross residual tumor unable to be removed at surgery).

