#### **1.2.2** Assess overall survival

Endpoint: patients will be followed for survival for one year after completion of adjuvant nivolumab.

**1.2.3** Assess the response of tumors prior to surgery based on RECIST 1.1

Endpoint: patients will be assessed radiographically with CT or MRI scan or assessed clinically.

**1.2.4** Assess complete surgical resection

Endpoint: patients will be assessed at surgery to determine if complete surgical resection was achievable after neo-adjuvant treatment with nivolumab and HF10.

**1.2.5** Assess the safety and tolerability of neoadjuvant nivolumab and HF10 with adjuvant nivolumab in patients with metastatic melanoma.

Endpoint: patients will be monitored for adverse events (AEs) and serious adverse events (SAEs) related to either or both nivolumab and HF10.

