# 4.2 Number of Patients

The total number of subjects for all sites is initially planned as 20 patients. The primary endpoint of pathologic response rate, including pCR, is expected to be seen in 20% of patients, hence 4 of the planned 20 patients are expected to have a pathologic response including pCR. Only patients who receive the combination neo-adjuvant treatment, nivolumab and HF10, and have a surgical resection according to the study calendar will be considered evaluable. Patients who discontinue the study before surgery then will be considered non-evaluable and will be replaced per principal investigator discretion.

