5.1 Inclusion Criteria

# Yes/No (Response of "no" = patient ineligible)

- **5.1.1** Patients must be  $\geq 18$  years or older.
- **5.1.2** Patients must have stage IIIB, IIIC, or IVM1a (equivalent staging at time of enrollment via AJCC 7th edition) metastatic melanoma which is eligible for complete surgical resection.
- **5.1.3** Prior systemic, regional and radiation anticancer therapies must have been completed at least three months prior to enrollment. Prior therapies (including anti-PD-1 inhibitors) are allowed provided three months have elapsed from last dose.
- **5.1.4** Patients must be a candidate for intralesional therapy.
  - At least 1 injectable cutaneous, subcutaneous, or nodal melanoma lesion  $\geq 10$  mm in longest diameter

OR

• Multiple injectable melanoma lesions which in aggregate have a longest diameter of  $\geq 10$  mm

AND

- Must have no known bleeding diathesis or coagulopathy that would make intratumoral injection unsafe.
- **5.1.5** Patients must have an Eastern Cooperative Oncology Group (ECOG) performance status of 0 or 1.
- **5.1.6** Serum LDH level  $\leq$  1.5 upper limit of normal (ULN) within 28 days prior to enrollment.
- **5.1.7** Patients have adequate organ function within 28 days prior to enrollment, as defined in table 1 listed below.

Table 1: Adequate Organ Function Laboratory Values:

Protocol name: Phase II Neoadjuvant trial of Nivolumab in Combination with HF10 Oncolytic Viral Therapy in Resectable Stage IIIB, IIIc, IVM1a Melanoma (Neo-NivoHF10) Version Date: 22JUL2019 Principal Investigator: [name]

System	Laboratory Value
Hematological:	
Absolute Neutrophil Count ANC	≥ 1,500/uL
Platelets	≥ 100,000/uL
Hemoglobin	$\geq$ 9 g/dL
Renal	
Serum Creatinine OR measured calculated creatinine clearance (GFR may also be used in place of creatinine or CrCl)	$\leq$ 1.5 upper limit of normal (ULN) OR $\geq$ 60 mL/min for subject with creatinine levels $\geq$ 1.5 X institutional ULN
Hepatic	
Serum total bilirubin	$\leq$ 1.5 X ULN OR Direct bilirubin $\leq$ ULN for subjects with total bilirubin $\geq$ 1.5 ULN
AST or ALT	
 
≤ 2.5 X ULN OR
 
≤ 5 X ULN for subjects with liver metastases
 

- **5.1.8** Men and women of childbearing potential must agree to use adequate contraception from the time of consent through 7 months after final nivolumab study treatment.

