# 6.1.2 Surgery

Surgery will be performed within 28 days of completing neo-adjuvant therapy with nivolumab and HF10. Patients who cannot proceed to surgery will not be evaluable and will be replaced. Patients may be allowed to remain on study treatment at the discretion of the principal investigator.

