# **10 STATISTICAL CONSIDERATIONS**

The primary endpoint of pathologic response including pCR is expected to be seen in 30% of patients, hence 6 of the planned 20 patients are expected to have a pathologic response, including pCR.

Pathological response will be determined by assessing the tumor viability at baseline and at surgery. Samples will be scored as a percentage viability (0-100%). A pathologic complete response (pCR) will be defined as no viable residual melanoma cells in the surgical specimen. A major pathologic response will be defined as <50% viable tumor cells. A minor pathologic response will be defined as 50% or greater viable tumor cells, including specimens that have 100% viability at surgery. Pathologic response rate (pRR) will be defined as frequency of either pCR or a major pathologic response. Analysis will also be performed of baseline tumor biopsies and on treatment biopsies if available for comparisons with the surgical resection specimen.

The null hypothesis is that the pathologic response rate for patients receiving the treatment is 5% or less. The alternative hypothesis is that the pathologic response rate is 30%. With 20 evaluable patients there will be 59% power using an exact binomial test at the one-side 0.05 significance level if the true response rate is 20%, and 89% power at one-sided alpha = 0.05 if the true response rate is 30%. Four or more pathologic responses in up to 20 patients will be sufficient to reject the null hypothesis. In additional to the statistical test, a 95% exact binomial confidence interval for the pathologic response rate will be calculated.

Kaplan-Meier methods and associated confidence intervals will be used to analyze RFS and OS. All subjects assessed for relapse will contribute to this analysis.

The statistical analysis of the safety data will be descriptive and tabular in nature.

The statistical analysis of pathologic and correlative exploratory endpoints will be descriptive. No hypothesis tests will be performed for exploratory endpoints.

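### As the plan reads, the complete-resection rate leaves out patients who never reach surgery, so it does not register resectability lost before the operation and is biased upward whenever such patients exist.

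*Combined protocol and SAP*

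**What the plan says.** Complete surgical resection is secondary objective 1.2.4 of the combined protocol and SAP. Section 9.8 describes the assessment: "Patients will be assessed at surgery to determine if complete surgical resection was achievable after neo-adjuvant treatment with nivolumab and HF10". Section 1.2.4 words its endpoint the same way, and 9.8 adds the R0/R1/R2 scale. The failure category on that scale is tied to the operation: "R2 indicates inability to completely excise all clinical disease (i.e. gross residual tumor unable to be removed at surgery".

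Three other rules decide who can contribute:

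- Section 5.1.2 admits only patients with "metastatic melanoma which is eligible for complete surgical resection".
- Section 6.1.2: "Patients who cannot proceed to surgery will not be evaluable and will be replaced".
- Section 4.2 limits evaluability to those who receive the combination and "have a surgical resection according to the study calendar will be considered evaluable". It continues: "Patients who discontinue the study before surgery then will be considered non-evaluable and will be replaced per principal investigator discretion".

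Section 10 sets out a test and an exact interval for pathologic response, Kaplan-Meier methods for recurrence-free and overall survival, and descriptive summaries for safety and for pathologic and correlative exploratory endpoints. For complete resection it gives no denominator, expected rate, interval or analysis.

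**The concern.** The objective asks whether complete resection is still achievable after 12 weeks of treatment in people who could have been completely resected at the start. A patient who becomes inoperable in that time has a known outcome: not completely resected. The plan classes that patient as non-evaluable and enrols someone else.

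This differs from the primary endpoint. Without surgery there is no specimen, so pathologic response is unobserved. For complete resection, missing surgery because the disease has become unresectable is itself the failure, and excluding the patient discards an observed result.

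At stake is the one endpoint aimed at resectability. A regimen under which several patients become inoperable would report the same rate as a regimen under which none do, if the operated patients had the same margins. Recurrence-free survival does not fill the gap, because Section 9.3 starts its clock at complete resection.

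**Working it through.** **The plan's own figure.** The only design calculation concerns pathologic response: "With 20 evaluable patients there will be 59% power using an exact binomial test at the one-side 0.05 significance level" at a true rate of 20%, and 89% at 30%, rejecting at 4 or more responses in 20. With X ~ Binomial(20, p), power is P(X ≥ 4): 58.9% at p = 0.20 and 89.3% at p = 0.30. At the 5% null the attained one-sided alpha is 0.0159; a cut-off of 3 would give 0.0755, so 4 is correct. These figures reproduce, but they say nothing about complete resection, for which the documents state no target or power.

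**Who is counted.**

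1. All patients are judged completely resectable at entry (5.1.2).
2. The assessment takes place at surgery (1.2.4, 9.8).
3. Patients who cannot have surgery are non-evaluable and replaced (6.1.2); those who stop earlier are non-evaluable and may be replaced (4.2).
4. Nothing in 9.8 or Section 10 overrides this.

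An operated-only denominator follows as a firm inference; no section writes it down.

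**Size of the effect.** Let n = 20 be the operated patients, x the number with R0, and k the number who received at least one dose, did not reach surgery and were replaced. Only n comes from the plan (20 evaluable patients); x and k are assumptions, because the documents give neither.

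- Rate as the plan reads: x / n, which does not depend on k.
- Rate over all who started: x / (n + k).
- Overstatement: x/n − x/(n + k) = (x/n) × k/(n + k).

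Intervals are exact (Clopper-Pearson) 95%: lower limit Beta(0.025; x, N − x + 1), upper limit Beta(0.975; x + 1, N − x), where N is the denominator.

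| R0 among 20 operated | As the plan reads | k = 2 (N = 22) | k = 4 (N = 24) | k = 6 (N = 26) |
|---|---|---|---|---|
| 16 | 80.0% (56.3 to 94.3) | 72.7% (49.8 to 89.3) | 66.7% (44.7 to 84.4) | 61.5% (40.6 to 79.8) |
| 19 | 95.0% (75.1 to 99.9) | 86.4% (65.1 to 97.1) | 79.2% (57.8 to 92.9) | 73.1% (52.2 to 88.4) |
| 20 | 100% (83.2 to 100) | 90.9% (70.8 to 98.9) | 83.3% (62.6 to 95.3) | 76.9% (56.4 to 91.0) |

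Differences in percentage points for k = 2, 4, 6:

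- 16/20 R0: 7.3, 13.3, 18.5
- 19/20 R0: 8.6, 15.8, 21.9
- 20/20 R0: 9.1, 16.7, 23.1

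With k = 0 every difference is zero.

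**The case against.** A reader might infer that, since everyone is resectable at entry, the endpoint must come out close to 100% whatever the treatment does, or that it cannot discriminate at all. The documents do not support either reading. They give no R0 rate. Eligibility for complete resection at entry does not guarantee the negative microscopic margins that R0 requires. R1 and R2 can be recorded in any operated patient, so resectability found to be lost during the operation does lower the rate. What is missed is loss before the operation.

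The other side has further points:

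- **The denominator is not written.** Section 9.1 ties evaluability to pathologic response, and in 4.2 the evaluability rule directly follows the expected pathologic response rate. One could therefore argue that the handling of unoperated patients for 1.2.4 is simply unspecified. That is fair as far as it goes, but 6.1.2 is not limited to one endpoint and the assessment is placed at surgery. An analyst following the text would use operated patients.
- **Progression is seen elsewhere.** RECIST 1.1 response before surgery is a separate secondary objective (1.2.3), and overall survival is followed. Both can reveal harm from disease growth before surgery. Neither measures resectability: progressive disease may still be resectable.
- **The magnitudes are hypothetical.** This stands. No passage suggests how many patients will miss surgery, and the answer may be none.
- **It is a secondary endpoint with no hypothesis or decision attached.** This stands too, and limits the severity.

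**Conclusion.** The point holds as a one-directional bias. Under the evaluability and replacement rules, the reported rate answers a narrower question than 1.2.4 asks: how often resection was complete among patients who were operated on. It is too high as an answer to the question posed whenever a treated patient fails to reach surgery.

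With 20 operated patients and 2 to 6 replaced, the overstatement runs from about 7 points (16/20 R0, 2 replaced) to about 23 points (20/20 R0, 6 replaced). This rests on assumed R0 counts, assumed losses, and the inference that only operated patients enter the denominator. It also counts every replaced patient as not completely resected; if some missed surgery for reasons unrelated to their disease, part of the gap is not loss of resectability. The primary test, its cut-off and its power are unaffected. The change should be made, but the trial's main conclusion does not depend on it.

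**What to change.** In 1.2.4, 9.8 and Section 10:

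- Define the complete resection rate as the number of patients with an R0 resection divided by all patients who received at least one dose of neoadjuvant treatment, including those later replaced, with an exact 95% confidence interval.
- State that complete means R0. Section 9.8 does not say whether R1 counts, and its R1 entry gives no margin status and should be completed.
- Count every patient without an R0 resection as not completely resected, whatever the reason: progression, toxicity, death, withdrawal or refusal of surgery.
- Tabulate the reasons for no surgery.
- Keep the R0/R1/R2 distribution among operated patients as a supporting table.
- State that the evaluability rule in 4.2 and 6.1.2 does not apply to this endpoint, and reconcile the two sections, since one makes replacement discretionary and the other does not.

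The cost is wording. No extra patients or procedures are needed. The documents do not expressly require the reason for no surgery to be recorded, and Section 12 restricts data capture, so one case report form field may have to be added. The drawback is a somewhat lower reported rate, in which patients who miss surgery for unrelated reasons count as failures; the table of reasons makes that visible.

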## 9.9 Pathology

**Archival Tissue:** Archival tissue from tumor of lymph node will be used to confirm disease pathology and next generation sequencing per standard of care practice.

## 9.10 Stopping Rules

If two subjects experience a grade 4 or 5 toxicity thought to be at least possibly related to the study products the study will be paused. Enrollment will be closed until the safety issue is discussed with the medical monitor and DSMC. Enrollment cannot reopen without written approval from the DSMC chair.

# **10 STATISTICAL CONSIDERATIONS**

The primary endpoint of pathologic response including pCR is expected to be seen in 30% of patients, hence 6 of the planned 20 patients are expected to have a pathologic response, including pCR.

Pathological response will be determined by assessing the tumor viability at baseline and at surgery. Samples will be scored as a percentage viability (0-100%). A pathologic complete response (pCR) will be defined as no viable residual melanoma cells in the surgical specimen. A major pathologic response will be defined as <50% viable tumor cells. A minor pathologic response will be defined as 50% or greater viable tumor cells, including specimens that have 100% viability at surgery. Pathologic response rate (pRR) will be defined as frequency of either pCR or a major pathologic response. Analysis will also be performed of baseline tumor biopsies and on treatment biopsies if available for comparisons with the surgical resection specimen.

The null hypothesis is that the pathologic response rate for patients receiving the treatment is 5% or less. The alternative hypothesis is that the pathologic response rate is 30%. With 20 evaluable patients there will be 59% power using an exact binomial test at the one-side 0.05 significance level if the true response rate is 20%, and 89% power at one-sided alpha = 0.05 if the true response rate is 30%. Four or more pathologic responses in up to 20 patients will be sufficient to reject the null hypothesis. In additional to the statistical test, a 95% exact binomial confidence interval for the pathologic response rate will be calculated.

Kaplan-Meier methods and associated confidence intervals will be used to analyze RFS and OS. All subjects assessed for relapse will contribute to this analysis.

The statistical analysis of the safety data will be descriptive and tabular in nature.

The statistical analysis of pathologic and correlative exploratory endpoints will be descriptive. No hypothesis tests will be performed for exploratory endpoints.

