#### 1.2 Secondary Objectives and Endpoint

1.2.1 Assess recurrence-free survival

Endpoint: recurrence after surgery will be assessed by radiologic scans scheduled per section 8 and confirmed by biopsy.

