# 9.3 Recurrence Free Survival

Secondary objectives for this study include recurrence free survival, which is defined as the time from complete surgical resection to the date of the first confirmation of disease reoccurance or death (whichever comes first). Progressive disease will be based on irRC response criteria.

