## 9.6 **Overall Survival**

Patient survival will be collected for up to one year following the EOT visit. Survival will be calculated by the Kaplan-Meier method.

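### The only analysis set given for RFS and OS is patients assessed for relapse, which conditions OS on surgery and later assessment and conflicts with death as an RFS event

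*Combined protocol and SAP*

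**What the plan says.** Section 10 names both endpoints in one sentence, "Kaplan-Meier methods and associated confidence intervals will be used to analyze RFS and OS", and then gives the analysis set: "All subjects assessed for relapse will contribute to this analysis". This is the only statement of an analysis set for either endpoint.

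The endpoint definitions are elsewhere:

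- **RFS.** Section 9.3 defines it as the "time from complete surgical resection to the date of the first confirmation of disease reoccurance or death (whichever comes first"). Section 1.2.1 says how relapse is found: "recurrence after surgery will be assessed by radiologic scans scheduled per section 8 and confirmed by biopsy".
- **OS.** Section 1.2.2 says "patients will be followed for survival for one year after completion of adjuvant nivolumab", and Section 9.6 says "Patient survival will be collected for up to one year following the EOT visit", by the Kaplan-Meier method. Neither gives a time origin or a population.
- **Patients without surgery.** Section 6.1.2 says "Patients who cannot proceed to surgery will not be evaluable and will be replaced". Section 4.2 has a similar rule, with replacement at the principal investigator's discretion. Neither says whether these patients count for OS.

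**The concern.** For OS, the set is defined by something that happens after treatment starts. To be assessed for relapse, a patient must come through the neoadjuvant phase, have surgery and live to a later assessment. Early deaths are the patients most likely to be missing, so the curve would describe a group selected partly for having survived.

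For RFS, the set and the definition disagree. Section 9.3 counts any death after complete resection. Section 10 admits only patients who had a relapse assessment. A death between resection and the first assessment is an event under one section and absent under the other.

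At stake is whether the reported OS describes the patients who were treated, and whether two analysts following the text would produce the same RFS curve. With about 20 patients, one or two early deaths visibly move either estimate.

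**Working it through.** **Figures in the plan.** None is stated for RFS or OS. The plan's power figures concern the primary endpoint and do reproduce: with X ~ Binomial(20, p) and rejection at X ≥ 4, P(X ≥ 4) is 0.0159 at p = 5%, 0.589 at 20% (stated 59%) and 0.893 at 30% (stated 89%). Nothing below affects them.

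**Window to the first relapse assessment.**

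- Neoadjuvant treatment runs to day 84, and surgery follows no later than 28 days after that (Section 8, note 8).
- Scans are then about every 12 weeks, restarted by surgery (Section 8, note 12), so the first is taken at about 84 days after surgery.
- Day 0 to first scan: 84 + 0 + 84 = 168 days to 84 + 28 + 84 = 196 days, ignoring visit windows.
- Surgery to first scan: 84 days.

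**Conditioning on being alive at the assessment.** Assume exponential survival with true 2-year OS S. If only patients alive at G days count, the 2-year estimate is S(2 y)/S(G) = S^(1 − G/730.5). Example: S = 0.70, G = 196 gives S(G) = 0.70^(196/730.5) = 0.909 and 0.70/0.909 = 0.770.

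| True 2-year OS (assumed) | Day-0 origin, G = 168 | Day-0 origin, G = 196 | Surgery origin, G = 84 |
|---|---|---|---|
| 60% | 67.5% | 68.8% | 63.6% |
| 70% | 76.0% | 77.0% | 72.9% |
| 80% | 84.2% | 84.9% | 82.1% |
| 90% | 92.2% | 92.6% | 91.1% |

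The overstatement is 2.2 to 8.8 points from day 0 and 1.1 to 3.6 points from surgery.

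**Omitting patients who never have surgery.** This is a separate illustration, not to be added mechanically to the table. Suppose 20 patients are assessed and a fraction d of all treated are not, so treated n = 20/(1 − d), rounded up. Assume 2-year OS of 80% in the assessed.

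- d = 5%, n = 22, 2 omitted with 2-year OS of 40%: (20 × 0.80 + 2 × 0.40)/22 = 76.4%.
- d = 25%, n = 27, 7 omitted with 2-year OS of 40%: (20 × 0.80 + 7 × 0.40)/27 = 69.6%.
- If the omitted have 60% instead, the all-treated values are 78.2% and 74.8%. If they have 80%, there is no distortion.

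The plan would report 80% in each case. Both the attrition and the survival rates are assumptions.

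**RFS.** Section 2.1 cites recurrence of up to 60% at 18 months, so take 18-month RFS as 8/20 = 40.0%. Leaving out one early post-resection death gives 8/19 = 42.1%; leaving out two gives 8/18 = 44.4%. Recurrences found at the first scan are still counted, so the RFS effect is confined to deaths before any assessment.

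**The case against.** The strongest reply is that Section 10 says who contributes and does not expressly shut anyone out. Sections 1.2.2 and 9.6 describe survival follow-up without restriction, Section 9.1 ties evaluability to pathological response, and Section 6.1.2 lets patients who cannot proceed to surgery stay on study treatment at the principal investigator's discretion. This stands to the extent that exclusion is an inference. But a sole analysis-set sentence is what will be programmed, and no other text gives OS a set of its own.

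Second, guarantee time depends on an OS origin that is not stated, and on when the first assessment takes place. Physical examinations at the four-weekly adjuvant visits could detect relapse before the 12-week scan, which would shorten the window. This stands; the sizes above are conditional on it.

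Third, a reader might infer that patients who progress before surgery, or whose resection is R1 or R2, appear in no time-to-event result. The documents do not support that. Patients without complete resection fall outside RFS because Section 9.3 starts the clock there, not because of the Section 10 sentence. R1 and R2 patients who are scanned after surgery would be in the OS set.

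Fourth, a reader might infer that an event-free survival endpoint is required. No objective calls for one, and pre-surgical failure is already described by RECIST response (Section 9.4) and completeness of resection (Section 9.8).

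Finally, at n = 20 an uncensored estimate of 80% has a normal-approximation 95% interval of 1.96 × √(0.8 × 0.2/20) = ±17.5 points, wider than any bias shown. That is fair on scale, but the interval does not correct a systematic shift.

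**Conclusion.** The point holds as a should-fix on two secondary endpoints. As written, the one analysis set conditions OS on reaching surgery and a later relapse assessment, leaves OS without an origin or population of its own, and contradicts the RFS definition for deaths before any assessment.

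Conditioning on survival to an assessment, or dropping early deaths, can only raise the estimate. Omitting patients who never have surgery raises it further if they fare worse. The amount cannot be derived from the documents. About 2-9 points (day-0 origin) and about 1-4 points (surgery origin) at 2 years rest on assumed exponential survival, an assumed true OS of 60-90% and a first assessment at the 12-week scan.

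It would go too far to say that OS definitely carries 24-28 weeks of guaranteed survival, because that presumes a day-0 origin the plan does not state. It would also go too far to call the trial's conclusion compromised: RFS and OS have no hypothesis test or decision rule, and the primary endpoint, its test and its power are untouched.

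**What to change.** Replace the analysis-set sentence in Section 10, before any survival analysis is run, with one rule per endpoint:

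- **OS:** all patients who received at least one dose, from the date of first dose, censored at the date last known alive. Confirm that survival follow-up includes patients who are replaced or do not reach surgery.
- **RFS:** all patients with complete resection, from the surgery date. Deaths are events whether or not a relapse assessment took place. Living patients with no assessment are censored at surgery.
- **Reporting:** state how many treated patients did not reach complete resection.

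Event-free survival from first dose may be added as a sensitivity analysis, but it is optional. It would also need a choice of progression standard, since Section 9.3 uses irRC while Section 8, note 19, uses RECIST for treatment decisions.

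The cost is wording and a check that survival status is collected for patients who leave before surgery, with little or no new data. The downside is a slightly less favourable OS and RFS estimate.
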